## ***8. Remuneration***

Subjects will be compensated based on the procedures undertaken. Subjects will receive up to \$240. The compensation amount will be as follows:

- Virtual visits: \$50 for each follow-up testing session (4-week, 8-week) for a total of \$100
- In-person visits: \$70 for baseline and post-intervention testing session for a total of \$140

If during the study the study staff determines that the participant cannot safely complete the session, he/she will be asked to stop – but he/she will still receive \$35 for their time and effort.

Additionally, associated travel fees accrued by subjects to participate in the study (e.g. parking fees at SRH) will be covered by the Motion Analysis Laboratory.

## **7. **Risks and Discomforts****

TC is likely to be safe, as there have been no reports of serious adverse impacts in the TC literature. We experienced no serious adverse events in our pilot studies with COPD, heart failure, vestibulopathy, and osteopenic populations. However, there may be some potential expected risks to participants including the following:

1. TC and other motor tasks included in the clinical evaluations of balance and gait may cause some muscle soreness in highly deconditioned individuals. This soreness is likely to only last a short time. In addition, shortness of breath, dizziness, or falls are possible. However, these risks are unlikely and will be discussed in both the protocol and consent form.

2. Possible discomforts associated with using the sensors are the same as those experienced when wearing other wearable devices such as bracelets, watches and heart monitor straps. Prolonged use of the sensors may cause sweating and skin irritation.

There is a possibility that subjects could fall or trip during the experimental procedures, or that they may experience an allergic reaction or minor skin irritation to the band used to attach the sensors to the body. There is also a possibility that subjects may become fatigued or experience muscle soreness.

The risk of falling during the TC exercises and balance tests will be minimized by excluding subjects with balance impairments and risk of falls based on medical history, self-reported previous falls, and some clinical tests to assess potential balance impairments in study participants, whose outcome will be used by a rehabilitation specialist to determine if the subject can safely perform the TC exercises. If a subject falls during remote visits or TC practice, they will be referred to their physician or to urgent care as needed.

Fatigue and muscle soreness will be minimized by allowing subjects to rest at any point during the experimental procedures.

Subjects will be encouraged to contact MAL staff with any questions or concerns they may have at any time during the study or after its completion.

Overall, the potential risks to participants are modest and are likely to be viewed as reasonable in relation to the anticipated benefits to subjects and others.

When - according to a rehabilitation specialist during in-person testing, or research staff during virtual testing - subjects are unable to safely perform the TC exercises that are part of the experimental procedures, the experiment will end. Subjects will be told why the experiment must stop and will be advised to seek medical care if appropriate.

Subjects will be told that the study procedures may be associated with discomfort due to wearing the sensors and by fatigue/muscle soreness. In case subjects experience discomfort or excessive fatigue, they will be free to remove the sensors and end their participation in the study.

Unintentional loss/disclosure of Protected Health Information may occur and is considered a minimal risk due to the security measures enforced at SRH. Confidential information will be kept in a locked filing cabinet, on REDcap, and on password-protected computers in the MAL.

## **8. Benefits**

Study participants are not expected to directly benefit from their participation, but it is possible that subjects will experience some positive impact on cognition, physical and mental health as a result of their performing TC exercises, as has been shown in prior TC studies. Information gained during the study is expected to contribute to the development of systems to facilitate the deployment of TC-based interventions.

## **9. Statistical Analysis**

Descriptive statistics will be derived for all the above-described clinical assessment outcomes and correlations will be sought with the sensor-based estimates of the metrics of adherence, proficiency and safety derived using the previously developed algorithms. Exploratory statistical analyses will be performed to power future clinical studies aimed to test the relationship between the proposed metrics of adherence and proficiency and the clinical outcomes of the intervention. Whereas conclusive statistical analyses to explore such correlations are beyond the scope of the proposed project, the data collected in this pilot study are expected to provide justification for a future trial aimed to assess the efficacy of the Tele-TC Platform as a training system for older adults with mild cognitive impairments.

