## 2. Assessments (Visits #1B, #2, #3 and #4)

At *Visit #1B*, subjects will be instructed in how to use the tablet-based Tele-TC program. The mobile devices and the sensors will be provided to each participant and will be preprogrammed with all required software. It is worth emphasizing that, as part of the consent process, all subjects will be asked permission to be videorecorded during the assessments via Zoom Enterprise.

Visits will be divided into two components: 1) clinical assessments and 2) instrumented monitoring of TC performance.

The following clinical assessments will be performed during *Visits #1B and #4*.

The following questionnaires will be provided to the subjects through REDcap Survey with an email link. It will take around 45 minutes to complete all of the questionnaires.

- *Activities Specific Balance Confidence (ABC)*: 16-item self-report measure in which patients rate their balance confidence for performing activities.
- *PROMIS® (Patient-Reported Outcomes Measurement Information System) 29 (PROMIS-29)* instrument: 29-item questionnaire assessing each of the following domains: anxiety, depression, fatigue, physical function, pain interference, pain intensity, sleep disturbance, and ability to participate in social roles and activities. The instrument contains four items from each primary domain plus a single pain intensity rating.
- *Physical Activity Scale for the Elderly (PASE)*: self-reported level of physical activity in individuals aged 65 years or older during the previous 7 days.
- *Exercise Self-efficacy Questionnaire (SEE)*: A 9-item questionnaire that focuses on the self-efficacy expectations for exercise for older adults; specifically, the ability to continue to exercise despite barriers.

*Clinical assessments which take around 15 minutes will include tests such as:*

- *Trail Making Test A/B*: Executive function will be assessed using the Trail Making Test. Participants will be timed while sequentially connecting a series of numbered circles (part A), as well as connecting an alternating series of numbers and letters (part B). The adjusted trail making score (i.e., part B minus A, sec) is sensitive to changes in executive function and frontal lobe pathology in older adults. The trail making Test will be camera-recorded.

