- *Controlled Oral Word Association Test (COWAT)*: examines working memory span. COWAT requires the participant to produce as many words as possible that begin with a given letter of the alphabet (F,A,S). There is 1 minute allowed for each of the three letters. The score is the sum of all acceptable words produced in the three trials. COWAT has good reliability and validity. The test will be audio-recorded and transcribed to ensure accurate collection of subjects' verbal responses.
- *Digit Span Test*: widely used measure of short-term memory, i.e. the number of digits a person can absorb and recall in correct serial order. Two trials of eight number sequences

are read aloud. The number sequences start out easy, with just two numbers, and get progressively more difficult, the last being nine digits. Scores are based on the number of sequences correctly recalled (i.e., until the participant consecutively fails two trials of the same digit span length). BDS has good reliability and validity.

- *Grip Strength:* we will measure the grip strength of both upper limbs using a hand grip dynamometer. We will repeat the measure three times.
- *Instrumented and camera-recorded monitoring of balance in each leg separately:* Subjects will be asked to stand on one leg for 30 seconds.
- *Instrumented and camera-recorded Timed-Up-and-Go:* Subjects will be asked to stand up from a chair, walk at their normal speed around a cone, turn around, and come back to sit in the chair.
- *Instrumented and camera-recorded Timed-Up-and-Go dual task:* Subjects will be asked to complete the previous task while counting backwards by three.
- *Instrumented and camera-recorded Sit-to-Stand:* Subjects will be asked to stand up from a chair while keeping their arms crossed across their chest during 30 seconds.
- *Instrumented and camera-recorded monitoring of balance in both legs* with feet shoulder-width apart and as close as possible without touching.
- *Instrumented and camera-recorded monitoring of gait:* Subjects will be asked to walk back and forth for 2 minutes.
- *Instrumented and camera-recorded monitoring the miniBEST:* It is a shortened version of the Balance Evaluation System Test (BESTTest). It is a 14-item test scored on a 3-level ordinal scale. It aims to target and identify different balance control systems.

Instrumented and camera-recorded monitoring of TC performance will be performed during Visits #1B, #2, #3 and #4:

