- Participants will be instrumented with 5 sensors (one on each limb and one on the trunk) and they will be following the instructions from the Tele-TC platform.

Study staff will use Zoom to communicate with subjects during the visits done remotely. The performance of TC exercises will also be videorecorded and scored using the proficiency metric described in our preliminary studies section to provide a gold standard. We will try to use the sensors during the remote visits, but if it is not possible, we will document the reasons and continue the TC exercises only with video.

Subjects will be asked to don one Smart GeneActiv watch by ActivInsights\* on their wrist to monitor activity during approximately a week after visits #1B and a week before visit #4.

We will ask the participants to send the GeneActiv back to the lab after wearing it. We will be sending another GeneActiv about two weeks before visit #4.

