## ***7. Data variables analysis to be collected***

The primary outcomes of the study are the retention and the protocol adherence during the study, and the System Usability Scale collected post-intervention.

The exploratory outcomes will include the following:

- The ease of use of the Tele-Tai Chi platform measure with the qualitative interview collected post intervention.
- The changes in outcomes collected at baseline and post-intervention: the Activities-specific Balance Confidence (ABC) scores, PROMIS 29 scores, the Physical Activity Scale for the Elderly (PASE), the Trail Making Test A/B scores, Self-Efficacy Exercise (SEE) scores, the grip strength, the Controlled Oral Word Association Test (COWAT), the Digit Span Test, the Timed-Up-and-Go, the Timed-Up-and-Go dual task single leg stance, the Sit-to-Stand performance, the balance on both legs with feet shoulder-width apart, the balance on both legs with feet close to each other, the normalized-to-height stride length and stride time variability, the activity level, and the Mini-Balance Evaluation Systems Test (MiniBEST) collected only in individuals who are willing to be tested in the MAL.
- The changes in The Tai Chi proficiency scores collected at baseline, 4 weeks, 8 weeks, and post-intervention.

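### Video of the Tai Chi sessions is scored as the reference for proficiency, but Section 9 plans no comparison of the sensor score with it, and no supplied text masks the scorer to visit

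*Combined protocol and SAP*

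**What the plan says.** Section 6, item 2 (Assessments) states: "Instrumented and camera-recorded monitoring of TC performance will be performed during Visits #1B, #2, #3 and #4". The recordings are to be "scored using the proficiency metric described in our preliminary studies section to provide a gold standard". If sensors cannot be used at a remote visit, "if it is not possible, we will document the reasons and continue the TC exercises only with video".

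Section 5 schedules sensor-based proficiency at baseline, at about 4 and 8 weeks, and at 12 weeks. Section 6, item 3 adds that the platform collects training proficiency automatically during home practice. Section 6, item 7 lists as an exploratory outcome "The changes in The Tai Chi proficiency scores collected at baseline, 4 weeks, 8 weeks, and post-intervention", without saying whether the score comes from sensor or video. Aim 2 (Section 2) hypothesises reliable proficiency data and improvement over 12 weeks.

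Section 9 reads: "Descriptive statistics will be derived for all the above-described clinical assessment outcomes and correlations will be sought with the sensor-based estimates". The sensor estimates meant are those of adherence, proficiency and safety. The other analyses it names are exploratory ones to power later studies relating adherence and proficiency to clinical outcomes. The video score is not mentioned.

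**The concern.** A measure collected as the reference for proficiency enters no stated analysis. The first question in Section 1 is whether the system can follow adherence, proficiency and safety over time. For proficiency, part of the answer is whether the sensor score agrees with its reference and moves with it in older adults with mild cognitive impairment. Section 9 also expects the data to justify a later trial and to help power studies of proficiency against clinical outcomes. That use is weaker if agreement in these users is left unexamined.

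Masking matters because of the video's role. A scorer who knows the visit and expects improvement may score later clips higher. Part of a rise in the reference would then be expectation, and a faithful sensor would seem to miss part of the gain.

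**Working it through.** **1. Text check.** Section 9 names two kinds of analysis: descriptive statistics for clinical assessment outcomes with their correlations with sensor metrics, and exploratory analyses for powering future studies. Neither compares sensor with video. Elsewhere the word blind occurs only in the name of the cognitive screening test. The identifier in Section 11 codes the person, not the visit.

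**2. Paired data.** The plan gives no power or precision figure to reproduce.
- Planned assessments: 20 × 4 = 80.
- Withdrawals are limited to 20% (Aim 1, Hypothesis 1): 20 × 0.80 = 16 completers, and 16 × 4 = 64 assessments.
- The 4- and 8-week visits are virtual (Section 6, item 8). The ceiling on video-only assessments at these visits is 20 × 2 = 40 of 80, or 32 of 64 among 16 completers. This is a ceiling and not a forecast, because staff will try to use the sensors.
- Item 8 treats baseline and week 12 as in person. Item 7, however, has a measure "collected only in individuals who are willing to be tested in the MAL", so some participants may not be tested in the lab.

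**3. Precision of the proposed comparison.** Assumptions: scores scaled to SD 1 at one visit; independent sensor and video errors, each with variance 1 − ICC; n = 16.
- SD of (sensor change − video change) = √(4(1 − ICC)). At ICC 0.8 this is √0.8 = 0.894.
- 95% CI half-width = t(0.975, 15) × SD/√16 = 2.131 × 0.894/4 = 0.48 SD.
- At ICC 0.9 and 0.6 the half-widths are 0.34 and 0.67 SD. With n = 12 they are 0.40, 0.57 and 0.80 at ICC 0.9, 0.8 and 0.6.
- By the noncentral t at ICC 0.8, a sensor blind to a uniform true gain of 0.8 SD would be exposed in 92% of studies, and to one of 0.5 SD in 55%. The check finds only a large failure.
- Agreement itself, by simulation with true ICC 0.8 and 70% of true-score variance between persons: 95% of studies estimate 0.60 to 0.90 from two complete paired visits, and 0.64 to 0.88 from four.
- The sensor-video correlation of change scores under the same model has median 0.56, 95% range about 0.09 to 0.83, and p < 0.05 in about 63% of studies. That is imprecise but not empty.

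**4. Effect of an unmasked scorer.** Assume no true change and a scorer shift at week 12, with n = 16. The SD of video change is √(2(1 − r)) for within-person correlation r. The documents give no value for the shift. The table shows how often the video CI excludes zero; with no shift it is 5%.

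| Shift | r = 0.5 | r = 0.7 | r = 0.8 |
|---|---|---|---|
| 0.1 SD | 6.6% | 7.7% | 9.1% |
| 0.2 SD | 11.6% | 16.2% | 22.0% |
| 0.3 SD | 20.3% | 30.6% | 42.7% |

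With a 0.3 SD shift, a faithful sensor would be wrongly shown to differ from the video in 14.4%, 24.2% and 42.7% of studies at ICC 0.6, 0.8 and 0.9, again against 5%.

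**The case against.** **Masking touches no planned result.** Section 5 names the sensor as the proficiency measure, and that score is not open to scorer expectation. The video score enters no planned analysis. This stands. A reader might infer that the proficiency results themselves would be biased by an unmasked scorer; the documents do not support that. Masking protects the video reference, and it matters once the video is compared with the sensor or reported as a series.

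**Unseen text may answer the point.** Video scoring is referred to a preliminary studies section that is not supplied, and Section 9 relies on algorithms developed earlier. It cannot be said that the sensor was never validated or that no scorer rule exists. Still, collecting a new reference here suggests that a comparison in these users has value.

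**Proficiency change is already specified.** A reader might infer that the four-visit change has been left out of the plan. Section 6, item 7 names both outcome and time points, and the wording of Section 9 can be read generously to include it. The stricter reading rests on item 2: "Visits will be divided into two components: 1) clinical assessments and 2) instrumented monitoring of TC performance". Taken that literally, Section 9 would also omit the primary outcomes, so loose wording is the likelier explanation. What remains is a detail: which score forms the series, and what happens at video-only visits.

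**The comparison could still be done.** It is also tempting to say that the study cannot show whether the sensor is accurate. Paired data will exist and nothing forbids their use, so the fair statement is that the comparison is not planned. Nor is longitudinal monitoring confined to four visits, since proficiency is also captured in home practice; that gives more sensor data, but the plan provides no scored video for those sessions.

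**Conclusion.** The point holds as a cheap improvement of minor weight. Section 9 plans no use of the video reference, and no supplied text masks its scorer to visit. As written, the study is not set up to show whether the sensor score agrees with its reference in the intended users.

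No primary conclusion changes, and Aim 2 is exploratory, so estimates with confidence intervals are enough. Section 9 disclaims conclusive analysis only of the correlations between sensor metrics and clinical outcomes, so the disclaimer does not cover sensor-video agreement.

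The sizes rest on assumed inputs. An ICC of 0.8 with 16 completers gives the half-width of about 0.48 SD. The harm from an unmasked scorer depends on the shift: about 7–9% false signals in the video score at 0.1 SD and 20–43% at 0.3 SD, against 5%.

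**What to change.** 1. **Section 6, item 2.** State that video clips are coded, stripped of visit labels and scored in random order. This masks baseline and week 12 from each other where both are in person. For remote visits masking is partial, because the setting shows.
2. **Section 9.** On visits with both measures, add sensor-video agreement: ICC and limits of agreement with 95% CI, allowing for repeated visits. Add the difference between sensor and video mean change from baseline to week 12, with 95% CI. Report how many visits are video-only and how many lack video, since "all subjects will be asked permission to be videorecorded during the assessments via Zoom Enterprise". If the correlation of change scores is also given, report it with its CI and call it imprecise at n = 16.
3. **Minor clarification.** Report the four-visit proficiency change separately for sensor and video, so that video-only visits are not mixed into the sensor series.

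If the preliminary studies section already contains validation results or scorer rules, cite them here.

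Cost: some wording, and coding and shuffling of at most 80 clips. No new visits, participants or data are needed. Scoring must wait until clips are pooled, and there is a little more analysis. Masking should be settled before scoring starts, because clips scored with the visit known could be repaired only by rescoring.

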## **10. Monitoring and Quality Assurance**

Because this study's procedures pose minimal risk to the subjects, bimonthly data and procedural reviews by the PI in consultation with study staff will be sufficient to identify and ameliorate any potential safety issues. Any safety concerns about the equipment or testing protocol will be brought to the immediate attention of [name]. Study staff will conduct bimonthly audits to ensure compliance with regulatory requirements for study documentation.

Approval of protocol, informed consent procedures, and recruitment will be obtained from the IRB during annual reviews.

Adverse event reporting will be done according to Partners Human Research Policy. Remedial action to prevent reoccurrence of the event will be instituted prior to the resumption of study procedures.

Study staff will conduct quarterly audits to ensure compliance with regulatory standards for study documentation.

## 11. Privacy and Confidentiality

- Study procedures will be conducted in a private setting
- Only data and/or specimens necessary for the conduct of the study will be collected
- Data collected (paper and/or electronic) will be maintained in a secure location with appropriate protections such as password protection, encryption, physical security measures (locked files/areas)
- Specimens collected will be maintained in a secure location with appropriate protections (e.g. locked storage spaces, laboratory areas)
- Data and specimens will only be shared with individuals who are members of the IRB-approved research team or approved for sharing as described in this IRB protocol
- Data and/or specimens requiring transportation from one location or electronic space to another will be transported only in a secure manner (e.g. encrypted files, password protection, using chain-of-custody procedures, etc.)
- All electronic communication with participants will comply with Mass General Brigham secure communication policies
- Identifiers will be coded or removed as soon as feasible and access to files linking identifiers with coded data or specimens will be limited to the minimal necessary members of the research team required to conduct the research
- All staff are trained on and will follow the Mass General Brigham policies and procedures for maintaining appropriate confidentiality of research data and specimens
- The PI will ensure that all staff implement and follow any Research Information Service Office (RISO) requirements for this research
- Additional privacy and/or confidentiality protections

The MAL will assign each new subject an alphanumeric identifier, which will henceforth be the sole means of identification connected to their data. All data will be collected under this identifier and will be kept isolated from any personal health information. All data will be stored on REDcap. Information shared with individuals outside of Partners will be labeled using an alphanumeric identifier and will be devoid of personal health information.

Video recordings and photos will be stored securely in the MAL; only investigators listed on the study will have access to them. Patients will be given the choice to have video/photo material used for academic articles and presentations.

This project is supported by the National Institutes of Health via an STTR award to BioSensics (primary site) and the involvement of researchers at SRH and BWH. De-identified data will be shared with BioSensics.

